- To determine the acceptability of text messaging to encourage participation in a FIM program.

Study Hypotheses

Phase 1: Not applicable

Phase 2:

- Primary:
 - Navigation + UC (\pm text messaging) [experimental] will result in mean overall satisfaction of >3.5 (scale of 1-5 with 5 being very satisfied).
 - Text messaging + UC (\pm navigation) [experimental] will result in mean overall satisfaction of >3.5 (scale of 1-5 with 5 being very satisfied).
- Secondary:

- Hypothesis A: Navigation + UC (\pm text messaging) [experimental] will result in a greater mean number of FIM meals received in 3 months than UC (\pm text messaging) [control].
- Hypothesis B: Text messaging + UC (\pm navigation) [experimental] will result in a greater mean number of FIM meals received in 3 months than UC (\pm navigation) [control].

Study Design

Phase 1: Conduct **human-centered design sessions** with CR patients to adapt two enhanced support interventions to FIM programs: **A) navigation and B) text messaging**. Navigation will be adapted from approaches known to work for enhancing enrollment and participation in CR.²² Text messages will be based on behavioral science to promote initiation and engagement and adapted from previously studied text message libraries.³²

Phase 2: We will conduct a 2x2 factorial design **pilot randomized trial** in 84 CR participants to compare the efficacy of navigation and text messaging interventions for increasing participation in a FIM program (Table 1). All participants will experience usual care (UC): a MyChart message with links to the FIM program and study measurement-related text messaging in the Eureka Research Platform. Additionally, participants will be co-randomized 1:1 to A) navigation (present/absent) and B) enhanced text messaging (present/absent), such that 25% of participants will be allocated to each of the four intervention arms. The primary outcome will be the number of MTMs or MTGs for meals (termed “FIM meals”) received during the 3-month study period. We will also **evaluate the implementation** of the interventions through interviews, review of “artifacts” of implementation (e.g., meeting minutes, materials), and data on implementation inputs, activities, outputs, and outcomes using a logic model framework.³³

Table 1. Four arms of the 2x2 factorial trial

Usual care (UC)	UC + Navigation
UC + Text messaging	UC + Navigation + Text messaging

Endpoints

Phase 1: Not applicable

Phase 2:

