- Primary endpoint: Satisfaction with the intervention.
- Secondary endpoints include the number of FIM meals received in 3 months, the proportion of patients initiating and engaged in the FIM program (received at least 1 and 8 FIM meals in 3 months, respectively), number of CV events in 3 months, and changes from baseline to 3 months in self-efficacy, food security, healthy eating, quality of life, and Life’s Essential 8 CV risk factors.

Participant Selection

Inclusion Criteria:

1. Age 18 or older
2. Attended at least one cardiac rehabilitation session within the last year at UCSF or ZSFG
3. Has access to the internet or a smartphone
4. Able to communicate in English or Spanish
5. Resides in San Francisco County

Exclusion Criteria:

1. Enrolled in hospice
2. Unable to consent for self
3. Currently receiving Project Open Hand services

Study Procedures

Phase 1 Recruitment

We will send a MyChart message to current UCSF CR patients inviting them to participate in human-centered design sessions.

Phase 1 Screening and Consent

Patients who respond to the recruitment email will be screened for eligibility based on inclusion and exclusion criteria. Participants will be asked to provide written, informed consent.

Phase 1 Human-Centered Design Sessions

Participants will complete a brief REDCap survey about demographics. We will conduct human-centered design sessions with CR patients. The human-centered design process will iteratively proceed through 4 phases: discover, define, develop, and deliver. The process will follow principles of technology design for health equity.³⁴ We will conduct 3 design sessions with groups of 2-6 CR patients each, audio and video-recorded and transcribed for rapid qualitative template analysis.³⁵ Groups will be language-concordant. The first session will focus on discovery and definition of patient needs and behaviors related to FIM in the context of the Theory of Planned Behavior, following an interview guide.³⁶ Based on this information, we will refine the interventions. The second session will focus on feedback on drafts of the developed materials. If significant revisions are needed, an additional session will be added. The third session will focus on refining the intervention materials by asking participants to “walk-through” the experiences of navigation and receiving text messages. If significant revisions are suggested, additional sessions of iterative revision will continue.

Phase 1 Participant Compensation

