Patient Health Questionnaire – 9 ⁴⁵	Validated measure of depressive symptoms	EHR	x	x
General Anxiety Disorder - 7 ⁴⁶	Validated measure of anxiety symptoms	EHR	x	x
Tobacco use	Important CV risk factor in Life's Essential 8.	Eureka	x	x
Sleep hours	Important CV risk factor in Life's Essential 8.	Eureka	x	x
Blood pressure	Important CV risk factor in Life's Essential 8.	EHR	x	x
Weight/Body Mass Index (BMI)	Important CV risk factor in Life's Essential 8.	EHR	x	x
Cholesterol	Important CV risk factor in Life's Essential 8.	EHR	x	x
Hemoglobin A1c	Important CV risk factor in Life's Essential 8.	EHR	x	x
Self-reported minutes/week of moderate to vigorous physical activity	Important CV risk factor in Life's Essential 8.	Eureka	x	x
Steps/day	Objective measure of physical activity in people with available data.	Eureka	x	x
Six-minute walk distance ⁴⁷	Objective exercise capacity measure collected routinely as an outcome in CR programs.	EHR	x	x
Satisfaction with the intervention(s) ⁴⁸	Measure of acceptability.	Eureka		x
Net promoter score	Measure of acceptability	Eureka		x
Time and costs	Custom questionnaire to help estimate costs.	Eureka		x
Consumption of food	Custom questionnaire to report consumption of distributed food	Eureka		x
Cardiovascular Events	Events include CV hospitalizations for myocardial infarction, heart failure, stroke, and deaths.	EHR		x
Number of CR sessions attended	Attending a greater number of CR sessions is associated with greater benefit. ⁴⁹	EHR		x
Number of FIM meal units	Primary outcome of study. We will be able to determine this outcome in all participants. Because some participants will receive groceries and some participants will receive meals, we will define this outcome as a meal "unit" received from POH. A meal unit is defined as 7 packaged meals (delivery), 1 grocery box (delivery), 1 set (5 or 7) of packaged meals (pick-up), or 1 grocery distribution (pick-up). We will collect number of FIM meal units throughout participants' 3-month study participation and throughout their insurance authorization period.	POH		x

	We will also collect number of FIM meal units for their dependents, if applicable.			
--	--	--	--	--

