An SAE is defined as any AE occurring that results in any of the following outcomes:

- death
- a life-threatening adverse experience
- inpatient hospitalization or prolongation of existing hospitalization
- a persistent or significant disability/incapacity
- a congenital anomaly/birth defect

Other important medical events may also be considered an SAE when, based on appropriate medical judgment, they jeopardize the participant or require intervention to prevent one of the outcomes listed.

[Serious Adverse Experience Reporting](#)

We will document all SAEs that occur (whether or not related to study intervention). The collection period for all SAEs will begin after informed consent is obtained and end after procedures for the final study visit have been completed.

In accordance with the standard operating procedures and policies of the Institutional Review Board (IRB)/Independent Ethics Committee (IEC), the Principal Investigator will report SAEs to the IRB/IEC.

[Discontinuation and Replacement of Participants](#)

A participant may be discontinued from the study at any time if the participant or the Investigator feels that it is not in the participant's best interest to continue. The following is a list of possible reasons for discontinuation:

- Participant withdrawal of consent
- Participant does not meet final eligibility confirmation
- Participant not adherent to study procedures
- Adverse event occurs that indicates in the opinion of the investigator that it would be in the best interest of the participant to discontinue the study
- Protocol violation requiring discontinuation
- Lost to follow-up
- Death
- Funder or Institution request for early termination of study

A participant may be withdrawn from the study at any time if the participant or the investigator feels that it is not in their best interest to continue.

All participants are free to withdraw from participation at any time, for any reason, specified or unspecified, and without prejudice.

Reasonable attempts will be made by the investigator to document a reason for participant withdrawals. The reason for the participant's withdrawal from the study will be specified in the participant's file source documents.

Participants who withdraw from the study after randomization may not be replaced.

Protocol Violations

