A protocol violation occurs when the participant or investigator team fails to adhere to significant protocol requirements affecting the inclusion, exclusion, subject safety and primary endpoint criteria.

When a protocol violation occurs, it will be discussed with the investigator and a Protocol Violation Form detailing the violation will be generated. This form will be signed by the Investigator. A copy of the form will be filed in the site's regulatory binder.

Data Safety Monitoring

This minimal risk study will not have an external Data Safety Monitoring Board. The Principal Investigator will monitor study data for completeness and monitor and report adverse events as described above.

Analysis Methods

Phase 1: We will qualitatively describe participant responses using rapid template analysis³⁵ based on the Theory of Planned Behavior³⁶ and emergent themes. At least two study staff members will review and code transcripts. Study staff members will meet to achieve consensus, with any disputes resolved by the Principal Investigator.

Phase 2: Respecting statistical norms for pilot studies, the proposed pilot randomized trial mimics the design we hope to use in the future and does not provide p-values or formal sample size calculations.⁵¹ The pilot study will provide information on the acceptability of the interventions. The sample size represents 1/3 of CR patients seen at UCSF in 9 months.

With a sample size of 42 for each experimental condition, this pilot study would be able to estimate a mean satisfaction score of 3.5 (scale of 1 to 5, with 5 being very satisfied) with a 95% confidence interval from 3.2-3.8, assuming a standard deviation of 1.

This pilot study will address two hypotheses (N=42 each) for the secondary outcome (which we expect to be the primary outcome for the future larger study):

Hypothesis A: Navigation + UC (\pm text messaging) [experimental] will result in a greater mean number of FIM meals received in 3 months than UC (\pm text messaging) [control].

Hypothesis B: Text messaging + UC (\pm navigation) [experimental] will result in a greater mean number of FIM meals received in 3 months than UC (\pm navigation) [control].

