For each intervention, the null hypothesis is the mean number of FIM meals received will not differ between experimental and control groups. Intervention-specific analyses will use separate generalized estimating equation (GEE) log-Poisson models with robust standard errors to estimate the mean (95%CI) count per group and experimental: control risk ratio (RR);⁵² models will be adjusted for the opposite experimental arm and baseline 6MWD as a measure of health status. An exploratory GEE model adding the A*B interaction term to models will be conducted and displayed in a forest plot of RR (95%CI) of each intervention arm (n=21) versus UC alone (n=21). Log-Poisson models will be used to estimate mean satisfaction and the proportions who initiated and engaged. We will use standard ANCOVA models to analyze 3-month changes in continuous outcomes (e.g., self-efficacy) and rank-based ANCOVA for changes in discrete outcomes (e.g., Life's Essential 8).⁵³ All ANCOVA models include the baseline value of the outcome as a covariate, the opposite experimental arm, and 6MWD.

We will also describe inputs, activities, outputs, outcomes using descriptive quantitative measures (e.g., counts, proportion, mean, standard deviation) and narrative description. We will qualitatively describe participant and staff responses from interviews and study artifacts using a rapid analysis template³⁵ based on the Theory of Planned Behavior,³⁶ Consolidated Framework for Implementation Research,⁵⁴ and emergent themes.

Cost Estimation

As part of this project, we will estimate costs of usual care and the interventions.

Usual care (costs may apply to all participants):

- Staff (health system): we will estimate the time it takes for staff to complete the following activities:
 - Draft MyChart message
 - Send MyChart message to participant
 - Complete and send referral for to POH
- Staff (POH): we will estimate the time it takes for staff to complete the following activities:
 - Receive and review referral from health system
 - Schedule participant intake
 - Conduct participant intake
 - Engage with participant during the course of the usual care program
- Participant: we will ask participants to estimate time and costs using a custom questionnaire, administered at the 3-month eVisit. Time and costs will be related to scheduling POH visits and receiving POH meals or groceries.

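### Does the pilot need a stated rule for judging whether mean satisfaction exceeds 3.5?

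*Combined protocol and SAP*

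**What the plan says.** The protocol synopsis and the Endpoints section make satisfaction with the intervention the primary endpoint of Phase 2. Under Study Hypotheses, navigation and text messaging each carry the same primary hypothesis, that the intervention "will result in mean overall satisfaction of >3.5 (scale of 1-5 with 5 being very satisfied".

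Analysis Methods, Phase 2, treats this endpoint in three places:

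- It states that the pilot "does not provide p-values or formal sample size calculations", and that its purpose is to inform on acceptability.
- It gives the expected precision for 42 participants per experimental condition: a mean of 3.5 "with a 95% confidence interval from 3.2-3.8, assuming a standard deviation of 1".
- It names the model: "Log-Poisson models will be used to estimate mean satisfaction and the proportions who initiated and engaged".

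The meal-count analysis, a few sentences before the last of these, uses "log-Poisson models with robust standard errors to estimate the mean (95%CI) count per group". The only null hypothesis in the section concerns the number of meals, which is a secondary outcome.

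**The concern.** A hypothesis with a numerical cut-off invites a yes-or-no answer. Without p-values, the answer has to come from the estimated mean and its confidence interval, and these can point different ways. A mean of 3.6 exceeds 3.5, but its interval runs from about 3.3 to 3.9 and does not exclude 3.5. One author could report the hypothesis as met and another as not shown, and the choice could be made after seeing the data. Because this is the primary endpoint, the omission looks more serious than it would for a secondary one.

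There is also a question of wording. The satisfaction sentence does not repeat the robust standard errors specified for the meal counts. Model-based Poisson errors would be too wide for a 1-5 rating with SD 1, and would enlarge the zone of disagreement.

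**Working it through.** **Inputs from the plan (Study Hypotheses; Analysis Methods, Phase 2).** Benchmark 3.5; n = 42 per intervention; SD = 1; 95% confidence.

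**Step 1: reproduce the stated interval.**
- Standard error = 1/√42 = 0.1543; half-width = 1.96 × 0.1543 = 0.302.
- Interval at a mean of 3.5: 3.198 to 3.802, which rounds to the stated 3.2-3.8.
- With a t quantile on 41 degrees of freedom: 3.188 to 3.812.
- Log-Poisson with robust errors, 3.5 × exp(±1.96 × 1/(3.5 × √42)): 3.21 to 3.82.
- Log-Poisson with model-based errors, 3.5 × exp(±1.96/√(3.5 × 42)): 2.98 to 4.11.

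The robust version agrees with the plan's figure to within rounding, and the model-based version does not. The plan's own precision statement therefore points to robust errors, and the missing words are only a matter of drafting.

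**Step 2: the zone where the two readings differ.** The point-estimate reading is met by any mean above 3.5. For the lower-limit reading, solve m × exp(−1.96 × SD/(m × √n)) = 3.5 for m.

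| n | SD | Smallest mean, robust log-Poisson | Smallest mean, t-interval |
|---|---|---|---|
| 42 | 1 | 3.79 | 3.81 |
| 42 | 0.8 | 3.73 | 3.75 |
| 42 | 1.2 | 3.85 | 3.87 |
| 34 | 1 | 3.82 | 3.85 |
| 30 | 1 | 3.84 | 3.87 |

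Only the first row uses the plan's own figures. The other SDs and responder counts are assumptions.

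**Step 3: how often the readings would disagree.** This uses 200,000 simulated samples of 42 integer ratings from 1 to 5 with SD 1 and the robust interval. The true means are assumed, since the documents give no expected value.

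| True mean | Point estimate above 3.5 | Lower limit above 3.5 | Disagree |
|---|---|---|---|
| 3.5 | 47% | 4% | 43% |
| 3.6 | 72% | 13% | 59% |
| 3.7 | 89% | 31% | 58% |
| 3.8 | 97% | 54% | 43% |
| 3.9 | 99% | 75% | 24% |
| 4.0 | 99.9% | 89% | 11% |
| 4.1 | about 100% | 96% | 4% |
| 4.2 | about 100% | 99% | 1.3% |

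The high rates occur only when true satisfaction is within about 0.3 of the benchmark, which is simply the half-width from Step 1.

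**Step 4: what depends on the answer.** The documents contain no progression or stopping criterion tied to 3.5. Analysis Methods says that the expected primary outcome of the future larger study is the number of meals, not satisfaction. The mean and its interval are computed in the same way under either reading.

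**The case for a change.** The strongest case for a change is that the plan chose to write hypotheses with a cut-off. Having given up p-values, it has only the estimate and interval with which to answer them, so it should say which one counts. If the true mean were exactly 3.5, so that the hypothesis is false, the point estimate would still exceed 3.5 in 47% of simulated trials, against 4% for the lower limit. Satisfaction is measured only at month 3 and withdrawn participants may not be replaced, so fewer than 42 responders is plausible and would widen the zone a little. A clarifying sentence would cost almost nothing.

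The omission and the arithmetic stand. The need for a rule does not follow from them. Requiring the lower limit to exceed 3.5 is in effect a one-sided 2.5% test, in a pilot that disclaims formal testing and was not sized for one. It would succeed in only 31% of simulated trials at a true mean of 3.7 and 54% at 3.8. Experienced statisticians would differ on whether to impose it. The alternative, declaring that the comparison is descriptive and showing the interval beside the mean, is what an estimation-based plan already implies. Giving the number of responders with each mean is routine reporting.

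**Conclusion.** The plan does leave unsaid how the benchmark of 3.5 is judged, and with n = 42 and SD 1 the two natural readings part for observed means from just above 3.5 to about 3.8. This is a gap that analysts will fill sensibly and not a fault that calls for a change. The estimate and interval are sound, the design is openly one of estimation, nothing in the documents is decided by the verdict on 3.5, and a reader given the mean and its 95% interval can see directly whether 3.5 is inside it.

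This conclusion rests on two things: that the interval is reported with the mean, as the precision statement implies, and that robust standard errors are used, as the stated 3.2-3.8 implies. The disagreement rates of 43% to 59% hold only for assumed true means of 3.5 to 3.8, and fall to 11% at 4.0 and 4% at 4.1. A real progression decision tied to 3.5 would change this view, but the documents contain none.

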Healthy eating prevents cardiovascular (CV) events.¹⁻⁴ Food is Medicine (FIM) interventions include medically tailored meals (MTMs), medically tailored groceries (MTGs), and nutritious food referrals.^{2,5} In people with chronic disease, FIM interventions improve quality of life, improve CV risk factors, reduce hospitalizations, and reduce healthcare costs.^{2,5-9} **Many questions remain about optimal approaches for referral, initiation, engagement, and retention in FIM programs to improve participation and ultimately health outcomes.²**

Cardiac rehabilitation (CR) is a guideline-recommended, multi-disciplinary program for people with heart conditions that includes nutrition counseling.^{10,11} The 12-week program is an opportune time for people to establish long-term habits. The CR population is well-suited for integrating and studying FIM programs because 1) CR patients are at risk for CV events, 2) FIM programs benefit people with CV conditions,⁵⁻⁷ and 3) CR patients are actively engaging in behavior change, which may be a beneficial time for engaging with a FIM program.¹²

Connecting CR and FIM programs offers a scalable opportunity to improve healthy eating and health outcomes in people with heart conditions. Our long-term goals are to optimize approaches for patients to engage in FIM programs and to examine the effects on health outcomes. Our central hypothesis is that **enhanced support for patients in addressing barriers to participation in FIM programs will improve engagement in FIM programs and health outcomes.** Formative and pilot studies are needed to adapt enhanced support interventions to diverse heart condition patients to inform future larger scale studies to test the effects of these interventions on health outcomes.

Medically Tailored Meals (MTM): MTMs improve outcomes for those with heart conditions, especially those unable to plan, shop for and/or prepare healthy food. Studies of MTM show improvements in health-related quality of life, diet quality, self-efficacy, food security, and cardiovascular (CV) risk factors (e.g., blood pressure and cholesterol).^{7,13,14} Because of these results and pilot programs,¹⁵ California now includes MTMs as a Community Supports benefit through its state Medicaid program.

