Participants will receive \$200 per design session.

Phase 2 Recruitment

We will give a recruitment flyer to current UCSF CR patients and newly initiating CR participants informing them about Food is Medicine and offering the opportunity to participate in the study. Participants may also be recruited to the study from referrals from health care providers, phone call from a clinical research coordinator, or contact from a clinical research coordinator in the CR center. We will also send a MyChart message to UCSF patients who have had a CR visit within the last year. Participants who do not use MyChart will be mailed a paper letter. Participants will be informed that they are 1) eligible for referral to a Food is Medicine program, 2) potentially eligible for a research study testing different ways to help people participate in a Food is Medicine program, 3) able to participate in the Food is Medicine program, even if they do not

participate in the study. Participants interested in the study will be given a link to join the study, which will take them to the Eureka Research Platform.

In addition, we will recruit participants who have completed at least one CR session at Zuckerberg San Francisco General Hospital (ZSFG) within the last year. Participants at ZSFG may also be recruited to the study from flyers, word of mouth, or contact from a clinical research coordinator.

Phase 2 Screening and Consent

Participant screening, consent, and subsequent study participation will occur on the Eureka Research Platform. The participant will answer screening questions based on inclusion and exclusion criteria for eligibility confirmation. The participant will provide eConsent for this minimal risk study in Eureka.

Phase 2 Randomization

Consented participants will undergo two randomizations:

- A) Randomization to navigation or usual care (1:1)
- B) Randomization to text messages or usual care (1:1)

Participants will be considered enrolled in the study after randomization.

Phase 2 Blinding

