The randomization groups of the participant will not be explicitly disclosed to the participant. However, since the interventions are different from usual care, it is possible that the participant may infer randomization group. Study staff delivering the navigation intervention will not be blinded to group allocation for navigation, since this will not be possible for the delivery of the intervention. Study staff will be blinded to text-messaging intervention. POH staff determining the number of meals received will be blinded to participant randomization groups.

Phase 2 eVisits

Participants will complete 2 study eVisits on Eureka. eVisit 1 will occur at the time of randomization. eVisit 2 will occur 3 months after randomization. Participants will complete questionnaires in Eureka (Table 2). If participants have connected health data (e.g., Fitbit, Apple Watch), they will be asked to contribute this optional data. In addition, study staff will abstract the electronic health record (EHR) for additional data (Table 2). After the final eVisit, the meals outcome data will be entered into Eureka via a coordinator form based on POH records. If participants are unable to complete eVisits on Eureka, a clinical research coordinator may call participants to complete surveys over the phone and enter data into Eureka via proxy data entry.

Table 2. Study Measurements

Measurement	Rationale	Source	Month
			0 3
Demographics and Health literacy ^{37,38}	Understand characteristics of participants.	Eureka	x

Medical conditions	Understand characteristics of participants.	Eureka	x	
Subjective social status ³⁹	Important social determinant of health.	Eureka	x	
Income and financial security	Important social determinant of health	Eureka	x	
Barriers to healthy eating (adapted)	Directly relevant to effects of intervention.	Eureka	x	x
Food security ^{40,41}	Important social determinant of health, directly relevant to potential effects of FIM programs.	Eureka	x	x
Mediterranean Eating Pattern Assessment (MEPA) ⁴²	Validated measure of diet quality, included in Life's Essential 8.	Eureka	x	x
Quality of Life (EQ-5D-5L)	Validated quality of life questionnaire that can be used to support cost effectiveness analysis. ⁴³	Eureka	x	x
General health status	Measure of general health status.	Eureka	x	x
Cardiac Self-efficacy ⁴⁴	Important behavioral science construct that may be influenced by the interventions.	EHR	x	x

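### Cardiac self-efficacy change, a named secondary endpoint, relies on EHR records that no study procedure creates; secondarily, the adjusted models need an EHR 6MWD with no rule for missing values

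*Combined protocol and SAP*

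**What the plan says.** The Endpoints section lists among the secondary endpoints "changes from baseline to 3 months in self-efficacy, food security, healthy eating, quality of life" and the Life's Essential 8 factors. The Analysis Methods section says "We will use standard ANCOVA models to analyze 3-month changes in continuous outcomes (e.g., self-efficacy" as the worked example, each model adjusting for the baseline value, the other intervention and 6MWD.

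Table 2 justifies cardiac self-efficacy as "Important behavioral science construct that may be influenced by the interventions" and gives its source as the EHR at months 0 and 3. Food security, MEPA and EQ-5D-5L, by contrast, come from Eureka at both months. Under Phase 2 eVisits, "In addition, study staff will abstract the electronic health record (EHR) for additional data (Table 2", and "eVisit 2 will occur 3 months after randomization". The Synopsis makes all Phase 2 visits remote.

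On who can enrol, the inclusion criterion is "Attended at least one cardiac rehabilitation session within the last year at UCSF or ZSFG". Recruitment covers current and newly starting CR patients, and adds: "We will also send a MyChart message to UCSF patients who have had a CR visit within the last year". The Background says of CR: "The 12-week program is an opportune time for people to establish long-term habits".

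The meals models adjust for baseline 6MWD. Table 2 sources 6MWD from the EHR and describes it as a routine CR outcome measure; it makes no such statement for self-efficacy. Table 2 also says that the meals outcome can be determined for everyone. No window for EHR values and no rule for a missing covariate is given.

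**The concern.** Abstraction can only retrieve what someone else recorded. The documents do not say how or when a self-efficacy score enters the EHR, and the remote study visits do not produce one. For a participant who has left CR, no described event would create a month-3 score, and the latest earlier score could be many months old. The endpoint could then describe mainly people still in CR or just out of it, with wider intervals than 84 participants would suggest. An answer not collected at month 0 cannot be recovered later.

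The 6MWD problem is separate and smaller. The value is a covariate and is probably available for many, but entry does not require it. If the software drops incomplete rows, participants whose meal counts are known leave the meals model. The plan expects meals to be the primary outcome of the larger study.

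**Working it through.** **The plan's own precision figure.** For satisfaction with n = 42 and SD = 1: 3.5 ± 1.96 × 1/√42 = 3.5 ± 0.30, or 3.2 to 3.8. This reproduces the stated interval and is not in dispute. The plan gives no precision figure for self-efficacy and no missingness rate for any EHR item, so every rate below is an assumption.

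**Age of the last CR contact at eVisit 2** (3 months, about week 13).
- In CR at randomisation and completing 12 weeks: CR ends between week 0 and week 12, so the last session is about 1 to 13 weeks old.
- Already finished, up to 52 weeks earlier: 13 to 52 + 13 = 65 weeks old. The upper end is the edge of eligibility.

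**Share already out of CR at randomisation.** Assume steady CR starts and full 12-week attendance. People with a session in the last 52 weeks started within the last 52 + 12 = 64 weeks, and those who started more than 12 weeks ago have finished: 52/64 = 81%. If a fraction f is recruited at CR start and the rest evenly from this pool, the share is (1 − f) × 81%: 61%, 41%, 20% and 0% for f = 25%, 50%, 75% and 100%.

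**Self-efficacy ANCOVA.** For a balanced two-level factor, SE = 2/√n in residual SD units. The 95% half-width uses t with n − 5 degrees of freedom (intercept, two interventions, baseline value, 6MWD). Month-0 scores and 6MWD are taken as present.

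| Month-3 value available | n | SE | t | Half-width | SE against n = 84 |
|---|---|---|---|---|---|
| 100% | 84 | 0.218 | 1.990 | 0.43 | – |
| 75% | 63 | 0.252 | 2.002 | 0.50 | +15% |
| 50% | 42 | 0.309 | 2.026 | 0.63 | +41% |
| 25% | 21 | 0.436 | 2.120 | 0.93 | +100% |

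**Missing 6MWD.** Let m be the share without a value. Dropping those rows multiplies the SE by 1/√(1 − m). Mean imputation with a missing indicator keeps all 84 and, in a linear model, multiplies the full-data SE by √(1 + m·r²/(1 − r²)), where r is the 6MWD–outcome correlation. Both assume that 6MWD is missing at random.

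| m | n if dropped | Per arm (planned 21) | SE, rows dropped | SE, imputed: r = 0.3 | r = 0.5 | r = 0.6 |
|---|---|---|---|---|---|---|
| 10% | 76 | 19 | +5% | +0.5% | +2% | +3% |
| 20% | 67 | 17 | +12% | +1% | +3% | +5% |
| 40% | 50 | 13 | +29% | +2% | +6% | +11% |

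For example, at m = 40% and r = 0.5: √(1 + 0.4 × 0.25/0.75) = 1.065; dropping rows gives 1/√0.6 = 1.291.

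**The case against.** The strongest reply is that no loss is demonstrated. Recruitment first names current and newly starting CR patients, and the past-year message is an added route. Someone just starting CR would finish about a week before eVisit 2, and a record from the end of the programme would be a reasonable month-3 value. For that group the EHR route may work well. A reader might infer from the 81% that most self-efficacy data will be missing. The documents do not support that: the figure needs enrolment drawn evenly from a full year's pool, and being out of CR makes a missing or old value possible rather than certain.

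It can also be said that Eureka would not deliver 84 of 84. eVisits can be missed, and withdrawn participants may not be replaced. This stands: the gain is Eureka completion minus EHR availability, and neither is known.

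On 6MWD, routine collection in CR suggests that many participants have a value. The plan nowhere prescribes complete-case fitting; that is an inference from common software behaviour. This also stands, and it makes the covariate issue secondary.

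The Data Collection Instruments section prefers Eureka questionnaires for participant-oriented outcomes where possible. That supports moving the scale, but a general preference does not override the source that Table 2 assigns.

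Finally, blood pressure, BMI, cholesterol and HbA1c are also EHR-only and share the exposure. That is true, but they are measurements, which a questionnaire item cannot simply replace.

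**Conclusion.** The point holds as a gap in how one secondary endpoint is secured. The text shows that nothing guarantees a timely self-efficacy score for participants who finished or left CR before randomisation. It does not show how many they are: 0% to 81% out of CR, the top being an extreme. The cost is precision (half-width 0.43 rising to 0.50, 0.63 or 0.93 residual SD if 75%, 50% or 25% have a month-3 value) and representativeness.

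Two stronger readings should be resisted. Bias between arms would need the availability of a month-3 record to differ by arm, and nothing in the documents suggests that. Nor is the source of the primary endpoint affected: the Endpoints section names satisfaction, which is collected in Eureka. Whether its model adjusts for 6MWD is not stated.

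The missing-6MWD rule is a secondary gap. It matters only if values are missing and incomplete rows are dropped. In a pilot that reports intervals without p-values, both changes are cheap improvements.

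**What to change.** 1. Administer the Cardiac Self-efficacy questionnaire in Eureka at both eVisits, as is done for MEPA and EQ-5D-5L, and change its Table 2 source from EHR to Eureka. The cost is a slightly longer questionnaire at two existing eVisits (the documents do not give its length). Missed eVisits will still leave some values missing.

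2. Add to Analysis Methods: *In all models that adjust for 6MWD, baseline 6MWD is the last value before randomisation within [window to be specified by the sponsor]. Where there is none, the mean of the observed baseline values is imputed and a missing indicator is added, so that no participant is dropped for lack of a 6MWD.* The reference to all models matters because the ANCOVA sentence does not say baseline, while Table 2 lists 6MWD at both months. Whether a pre-randomisation value exists cannot depend on the arm, so this simple method is sound here. Its precision cost depends on the 6MWD–outcome correlation: with 40% missing, about 2%, 6% or 11% at r = 0.3, 0.5 or 0.6, against about 29% if rows are dropped.
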